9.2.2 RCT OF NDURE VERSUS USUAL CARE

Power and sample size calculations were performed using PASS v08.0.13, “Inequality Tests for Two Independent Proportions.” The primary endpoint for this pilot RCT is the rate of PORT delay, defined as starting PORT > 6 weeks after surgery. Our primary objective is to compare PORT delay rates between the NDURE and usual care arms. We hypothesize that, compared with patients who receive usual care, patients who receive NDURE will have a decreased rate of PORT delay (initiation of PORT > 6 weeks after surgery). Alternatively, our null hypothesis is that there will be no difference in the rate of PORT delay between NDURE and usual care. We assume the rate of PORT delay in the usual care arm will be 45%⁴⁵ and target an absolute reduction in PORT delay of 20% (rate of PORT delay in the NDURE arm = 25%)²⁴. This effect size is clinically significant and realistic given results in similar (non-randomized) interventions²⁴. Seventy-five patients in each arm yields 83% power to detect a 20% reduction in PORT delay (45% versus 25%) based on a two-sided Z-test with pooled variance of two independent proportions assuming a two-sided $\alpha = 0.1$. Our selection of $\alpha = 0.1$ and $1 - \beta = 0.8$ is based on the desire to emphasize power over type I error at this early stage of development (single-site pilot RCT) to ensure follow-up on promising interventions. Furthermore, given the trial’s design, comparison of PORT delay rates between

trial arms will be analyzed using a model-based approach (discussed in Section 9.4.3.2) with inclusion of randomization stratification variables as model covariates, an analytic approach which preserves the type I error rate at nominal α , and increases power relative to an unadjusted model.⁶¹ Therefore, our power analysis based on a Z-test is conservative, and we anticipate even greater power based on our analytic plan. We therefore consider our RCT to be appropriately and rigorously designed to detect a clinically meaningful reduction in PORT delay. In order to have 150 patients eligible for the PORT delay analysis set (see Section 9.3, Population for Analyses), we plan to enroll 170 patients. Our sample size is inflated by 17% based on historical data. If at 170 patient accruals we have not achieved 75 patients evaluable for the primary endpoint in each arm, we will continue to enroll until we have achieved either accrual of a minimum of 75 evaluable patients in each arm or have accrued a maximum of 180 total patients.

9.3 POPULATIONS FOR ANALYSES

The safety analysis set (SAS) is composed of all patients enrolled who receive any part of either the NDURE or UC intervention. The SAS will be used to conduct all safety analyses. Patients will be analyzed based on the intervention received regardless of the assignment at randomization.

The PORT delay analysis set is composed of all patients enrolled in the trial who are:

1. Randomized to NDURE or UC
2. Receive curative intent surgery at MUSC
3. Have an indication for PORT per NCCN Guidelines based on the presence of at least one of the following adverse features on final pathologic evaluation: ENE, positive margin, pT3 or pT4 primary, at least pN1 nodal disease (per AJCC 8th edition for p16-ve non-oropharyngeal SCC or AJCC 7th edition for p16+ve oropharyngeal SCC), nodal disease in levels IV or V, PNI or LVI
4. Are alive for ≥ 6 weeks postoperatively.

Analysis will be performed based on assignment at randomization regardless of the intervention received (modified intent to treat). This analysis set will be used for analysis of the primary endpoint. The rationale for this definition of the PORT delay evaluable set is that eligibility, randomization, and delivery of a portion of the intervention occur prior to definitive treatment of the HNSCC. However, the primary endpoint is evaluable only for patients who undergo surgery for HNSCC, have an indication for adjuvant PORT (which can only be definitively known following surgical resection), and are alive for at least 6 weeks postoperatively. Therefore, we expect that a subset of patients who meet all eligibility criteria will be enrolled in the study, randomized to NDURE or UC, receive a portion of the intervention, but subsequently be non-evaluable for the primary endpoint when information becomes available later in the clinical course that cannot be known at the time of study enrollment and randomization (e.g., they (1) elect a non-surgical treatment option; (2) have no indication for PORT per NCCN Guidelines on final pathologic assessment; (3) have a mortality prior to 6 weeks postoperatively).

The Time-to-PORT (TTP) analysis set is composed of all patients enrolled in the trial who are:

1. Randomized to NDURE or UC
2. Receive curative intent surgery at MUSC
3. Have an indication for PORT per NCCN Guidelines based on the presence of at least one of the following adverse features on final pathologic evaluation: ENE, positive margin, pT3 or pT4 primary, at least pN1 nodal disease (per AJCC 8th edition for p16-ve non-oropharyngeal SCC or AJCC 7th edition for p16+ve oropharyngeal SCC), nodal disease in levels IV or V, PNI or LVI

Analysis will be performed based on assignment at randomization regardless of the intervention received (modified intent to treat). This analysis set will be used for analysis of the secondary endpoint TTP.

The **treatment package time (TPT) analysis set** is the TTP analysis set restricted to patients who have initiated PORT.

The **full analysis set (FAS)** is the set of all trial participants who enroll and are eligible for the study. Patients who enroll but subsequently drop out prior to receiving any of the assigned intervention will be replaced. The FAS will be used for evaluation of the pre-surgical radiation consultation, and for secondary analyses of both the primary endpoint and secondary endpoints.

The **dental evaluation prior to surgery analysis set** will be the FAS restricted to patients who receive curative intent surgery at MUSC and are indicated for dental evaluation.

The **extraction of indicated teeth analysis set** is the subset of patients in the dental evaluation prior to surgery analysis set who are indicated for dental extractions prior to surgery.

The **time from surgery to PORT referral scheduling analysis set** and **time from surgery to appointment with radiation oncology analysis set** are equivalent to the TTP analysis set.

The **Per protocol set** is composed of all patients enrolled in the trial who have completed all 3 of the ENDURE intervention sessions as described in the protocol. This analysis set will be used for secondary analyses of both the primary endpoint and secondary endpoints.

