Study Population:	The study population will consist of patients 18 years of age or older, male and female sex, and self-identified white and AA race, with locally advanced HNSCC undergoing curative intent surgery followed by PORT with or without concurrent chemotherapy.
Phase/Stage:	N/A
Description of Sites:	The study will be conducted, and participants enrolled, at the Medical University of South Carolina (MUSC) Hollings Cancer Center (HCC) Head and Neck Tumor Center.
Description of Study Intervention:	NDURE is a navigation-based, MLI targeting barriers to timely, guideline-adherent PORT at the patient-, healthcare team-, and organization-levels to decrease delays and racial disparities starting guideline-adherent PORT. NDURE will be delivered from surgical consultation to PORT initiation (~3 months). The three NDURE navigation sessions, which are expected to take 30-60 minutes each, will coincide with the presurgical consult, hospital discharge, and 1 st postoperative clinic visit, time points chosen to facilitate case identification and coordination across key care transitions.
Study Duration:	NDURE Feasibility: 7 months NDURE vs Usual Care RCT: 42 months
Participant Duration:	3 months

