
^a Study Visit 5 assessments are to be administered after the start of PORT. For the purposes of determining when to administer Study Visit 5 assessments, the study coordinator will determine that a patient has started PORT either by verifying in the EMR (for patients undergoing PORT at MUSC) or by contacting the patient no sooner than 8 weeks after surgery (for patients undergoing PORT outside of MUSC). If PORT is indicated but never initiated, Study Visit 5 assessments are to be completed 12 weeks after surgery.
 
^b Following completion of PORT, the study coordinator will gather all of the required source documentation to ascertain efficacy and cancer care delivery endpoints as well as adjuvant therapy details
							

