To evaluate the preliminary clinical impact of NDURE compared with UC on delays starting PORT among white and AA HNSCC patients.	PORT delay, defined per National Comprehensive Cancer Network Guidelines as the initiation of PORT > 6 weeks (42 days) following definitive surgery for HNSCC.
Secondary	
To evaluate the preliminary clinical impact of NDURE compared with UC on time-to-PORT among white and AA HNSCC patients.	Time-to-PORT initiation, defined as the number of days from the date of definitive surgery for HNSCC to the date of initiation of PORT. Treatment package time, defined as the number of days from the date of definitive surgery for HNSCC to the date of PORT completion.
To evaluate the preliminary clinical impact of NDURE compared with UC on racial disparities in delays starting PORT among white and AA HNSCC patients.	PORT delay, defined per National Comprehensive Cancer Network Guidelines as the initiation of PORT > 6 weeks (42 days) following definitive surgery for HNSCC. Time-to-PORT initiation, defined as the number of days from the date of definitive surgery for HNSCC to the date of initiation of PORT.

Table 2. Study Objectives and Endpoints

	Treatment package time, defined as the number of days from the date of definitive surgery for HNSCC to the date of PORT completion.
To evaluate the preliminary impact of NDURE compared with UC on cancer care delivery processes.	Pre-surgical radiation consultation, defined as the attendance by the patient at a consultation with the treating radiation oncologist prior to surgery to discuss radiation therapy in the definitive or adjuvant setting.
	Pre-RT dental extractions, defined as the extraction of indicated carious/non-restorable teeth prior to or during definitive surgery.
	Time from surgery to PORT referral, defined as the time, in days, from the date of the definitive surgical procedure to the date the referral (or postoperative appointment) is placed to discuss adjuvant therapy with the treating radiation oncologist.
	Time from surgery to postoperative appointment with radiation oncology, defined as the time, in days, from the date of the definitive surgical procedure to the date that the patient attends a postoperative appointment with radiation oncology
Exploratory	

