9.4.2 MISSING DATA

- PORT delay status (delay or timely PORT) will be considered 'delayed' for any evaluable patient with missing PORT delay status.
- TTP will be right-censored for evaluable patients who die prior to PORT initiation, are lost to follow-up prior to PORT initiation, or who haven't received PORT by the end of follow-up (18 weeks postoperatively).
- TPT will be right-censored for evaluable patients who die or are lost to follow-up prior to the conclusion of PORT, or who prematurely discontinue their intended course of PORT. TPT will also be right-censored for patients who have not completed PORT by the end of follow-up (18 weeks postoperatively).
- Time from surgery to PORT referral scheduling will be right-censored for evaluable patients who die prior to PORT initiation, are lost to follow-up prior to PORT initiation, or who haven't received PORT by the end of follow-up (18 weeks postoperatively).
- Time from surgery to appointment with radiation oncology will be right-censored for evaluable patients who die prior to PORT initiation, are lost to follow-up prior to PORT initiation, or who haven't received PORT by the end of follow-up (18 weeks postoperatively).

- Analyses of exploratory endpoints will be conducted using complete case analysis.

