Treatment package time, NDURE vs UC: TPT is defined as the number of days between the date of definitive surgery and the date of PORT completion. Analysis will be conducted using cumulative incidence plots (1 – Kaplan-Meier plots) with Greenwood variance estimation to construct corresponding 90% CIs. Treatment group comparisons will be conducted using a stratified log-rank test adjusting for randomization stratification variables. TPT will be right-censored as described in Section 9.4.2. The hazard ratio comparing the two arms will be estimated using Cox proportional hazards regression controlling for stratification variables. A sensitivity analysis will be conducted treating deaths after PORT initiation but prior to the completion of PORT as a competing risk to evaluate the bias incurred in cumulative incidence estimation by right-censoring deaths. Analyses will be performed using the TPT analysis set.

Treatment package time (Black vs White) in NDURE vs UC: TPT cumulative incidence plots (1 – Kaplan-Meier plots) will be constructed for Black and White patients randomized to NDURE and for Black and White patients randomized to UC as described. Group comparisons will be conducted using a stratified log-rank test, but controlling only for predicted radiation facility as a randomization stratification variable since a race-by-trial arm interaction term is used to evaluate this hypothesis. A Cox proportional hazards regression model will be fit as described with appropriate race-by-trial arm interaction. Censoring rules will be as described in Section 9.4.2. A sensitivity analysis will be performed treating deaths after PORT initiation but prior to the completion of PORT as a competing risk. Analyses will be conducted using the TPT analysis set.

Time from surgery to PORT referral scheduling, NDURE vs UC: Time from surgery to PORT referral scheduling will be analyzed using the approach described for all time-to-event endpoints. Censoring rules will be as described in Section 9.4.2. Analyses will be performed using the time from surgery to PORT referral scheduling analysis set.

Time from surgery to appointment with radiation oncology, NDURE vs UC: Time from surgery to appointment with radiation oncology will be analyzed using the approach described for all time-to-event endpoints. Censoring rules will be as described in Section 9.4.2. Analyses will be performed using the time from surgery to appointment with radiation oncology analysis set.

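### The treatment package time analysis drops patients who never start PORT, so its comparisons are open to selection bias if NDURE changes who starts

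*Combined protocol and SAP*

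**What the plan says.** Section 3 (Table 2) lists TPT as a secondary endpoint of the RCT: "Treatment package time, defined as the number of days from the date of definitive surgery for HNSCC to the date of PORT completion". Section 9.3 builds its analysis set from the time-to-PORT (TTP) set, which holds randomized patients who had curative-intent surgery at the study centre and a pathologic indication for PORT. The TPT set "is the TTP analysis set restricted to patients who have initiated PORT". For the arm comparison of TPT, Section 9.4.4.2 states "Analyses will be performed using the TPT analysis set", and it names the same set for the race-by-arm comparison. Both use 1 – Kaplan-Meier curves, a stratified log-rank test and a Cox model.

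The plan expects that some patients will not start. A footnote to the Schedule of Activities (Section 1.3) reads "If PORT is indicated but never initiated, Study Visit 5 assessments are to be completed 12 weeks after surgery". For TTP, Section 9.4.2 keeps such patients and right-censors them; the rule covers those who die first, are lost, "or who haven't received PORT by the end of follow-up (18 weeks postoperatively"). The times to PORT referral and to the radiation oncology appointment use the same set and the same censoring rule.

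On the intervention, the synopsis (Section 1.1) gives its aim as "to decrease delays and racial disparities starting guideline-adherent PORT" and its timing as "NDURE will be delivered from surgical consultation to PORT initiation (~3 months").

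**The concern.** The TPT clock starts at surgery, but entry to the set depends on a later event. That event comes after randomization and after the navigation sessions, at the point in care that navigation is meant to influence. If NDURE brings to treatment some patients who under usual care would never have started, those patients enter the NDURE side of the comparison while their usual-care counterparts drop out. The two groups of starters then differ in case mix, and a difference in TPT can appear or vanish without any patient's package time having changed.

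The result will be used. The amendment history (Section 10.4, version 6.0) says TPT and related endpoints were added because of a worry that earlier starts could bring interruptions during radiation. Selection could produce a false signal of that kind, or hide a real shortening of TPT. The racial-disparity version rests on the same set.

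**Working it through.** **1. The plan's own figures.** The documents give no power, effect size or non-initiation rate for TPT. The only power figure is for the primary endpoint: 83% with 75 per arm, 45% versus 25%, two-sided alpha 0.10 (Section 9.2.2). It reproduces. The pooled SE is √(2 × 0.35 × 0.65 / 75) = 0.0779 and the unpooled SE is √((0.45 × 0.55 + 0.25 × 0.75) / 75) = 0.0762. Power is Φ((0.20 − 1.645 × 0.0779) / 0.0762) = 82.7%. This has no bearing on TPT.

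**2. How the plan treats patients who do not complete PORT.**

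| Patient with an indication | TTP, referral and appointment times | TPT |
|---|---|---|
| Never starts PORT | Kept, censored (9.4.2) | Left out (9.3) |
| Starts, then stops early | Kept | Kept, censored (9.4.2) |
| Dies before starting | Kept, censored (9.4.2) | Left out (9.3) |

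Two provisions might seem to cover the gap. The TPT sensitivity analysis in Section 9.4.4.2 treats as competing only deaths that occur after PORT has begun, so it does not reach non-starters. Section 9.3 also names the full analysis set for secondary analyses of secondary endpoints. It gives no TPT rule for non-starters there, and that set can include patients who never have surgery and so have no starting date for TPT.

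**3. Size under assumptions.** None of these inputs is in the documents. Usual starters have a median TTP of 41 days (log-normal, log SD 0.22). PORT lasts 44 days (SD 3). In each arm 5% never start. A further share f starts only under NDURE, at about day 70 (SD 8). Follow-up ends at day 126 (18 weeks).

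The mechanism can be checked by hand. Mean TTP in usual starters is 41 × exp(0.22² / 2) ≈ 42 days, so mean TPT is 42 + 44 = 86 days. The extra starters have mean TPT 70 + 44 = 114 days. With f = 10%, NDURE starters are 85 usual and 10 extra per 100 patients, so mean TPT is (85 × 86 + 10 × 114) / 95 = 88.9 days, against 86 days in usual care. That is a gap of about 3 days with nobody's time lengthened.

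An unstratified Cox model was then fitted to simulated data. A hazard ratio (HR) above 1 means faster completion under NDURE. HRs use 200,000 patients per arm. Error rates use 2,000 trials with 75 per arm before the filter, at two-sided alpha 0.10.

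| f | (a) No effect in usual starters: starters-only HR | (a) Trials wrongly finding longer TPT (nominal 5%) | (a) Non-starters kept: HR | (b) 4-day benefit in usual starters: starters-only HR | (b) Non-starters kept: HR |
|---|---|---|---|---|---|
| 0% | 1.00 | 4% | 1.00 | 1.39 | 1.30 |
| 5% | 0.86 | 21% | 1.07 | 1.14 | 1.32 |
| 10% | 0.74 | 48% | 1.15 | 0.97 | 1.37 |
| 15% | 0.67 | 72% | 1.22 | 0.84 | 1.45 |

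In (b) a real benefit disappears or reverses in the starters-only analysis; keeping non-starters removes the reversal. In (a), HRs above 1 with non-starters kept reflect the larger share who complete PORT under NDURE. With f = 0% and no effect, the filter creates no difference.

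**4. Horizon.** Section 9.4.2 censors TPT at 18 weeks, whereas Section 4.2.4 follows patients for 365 days. Taking the 6-week radiation course mentioned in Section 6.1.1.1, a patient who starts after day 126 − 42 = 84 cannot be seen to complete by day 126. The choice of horizon therefore decides how late starters count.

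**The case against.** The strongest reply is that the premise is inferred. The stated target of NDURE is the timing of PORT, and the hypotheses in Section 9.1.2 concern delay beyond 6 weeks and median TTP. Nowhere is NDURE said to change the share who ever start. This stands: the bias is conditional on such a change, and its size cannot be had from the documents. The large shifts above rest on assumed shares and an assumed late start.

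Restriction also answers a legitimate question. Interruptions of radiation can arise only in patients who begin it, and a package time ending at completion has no natural value for those who do not. That is a reason to keep the starters-only analysis, though not as the main one. Section 3 already has an exploratory endpoint, PORT duration among completers, for the duration question.

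Three stronger readings should be resisted:

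- A reader might infer that TPT cannot be interpreted by randomized arm at all. The parent TTP set is analysed by assignment and is already an openly modified intent-to-treat set, conditioned on surgery and pathology. The PORT-start filter adds one more selection step, nearer to what NDURE acts on.
- A reader might infer bias in either direction. Only bias against NDURE has been shown; no route to a false benefit has been worked out.
- A reader might size the problem by completion proportions. If 10% and 3% never start and 90% of starters complete, completion is 0.90 × 0.90 = 81.0% versus 0.97 × 0.90 = 87.3% overall, and 90% versus 90% among starters. The planned analysis is 1 – Kaplan-Meier with early discontinuers, deaths and losses censored, so it would not show those figures.

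**Conclusion.** The concern holds in a conditional form. The plan conditions a secondary endpoint counted from surgery on an event that follows randomization and navigation, and its TPT analyses contain no remedy. If NDURE alters who starts PORT, the arm and race-by-arm comparisons are subject to selection bias, most plausibly against NDURE. If starters are comparable across arms, there is none. The HR range of 0.86 to 0.67 illustrates 5 to 15% starting late and only because of NDURE; it is not an estimate for this trial. One secondary endpoint of a pilot trial, with no stated power, is affected, and the primary analysis does not use this set.

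**What to change.** In Sections 9.3, 9.4.2 and 9.4.4.2:

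- Make the TTP analysis set, by randomized arm, the main set for both TPT comparisons.
- Keep patients who never start PORT at risk, as not having completed it, up to one common horizon. Treat patients who stop PORT early in the same way instead of censoring them at discontinuation.
- Treat death before completion as a competing event, whether or not PORT has begun.
- Choose the common horizon by reconciling the 18-week TPT censoring in Section 9.4.2 with the 365-day follow-up in Section 4.2.4.
- Report the number of non-starters by arm, and by race within arm.
- Keep the starters-only analysis, labelled supportive.

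This is a cheap improvement. It needs SAP wording only, because the Schedule of Activities already collects PORT start and completion dates. The downside is that TPT then combines initiation with duration. If start rates are equal, a real benefit is slightly diluted (HR 1.39 to 1.30 in the assumed example), which is why the starters-only result should still be shown.

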6.1.1.2 USUAL CARE

The processes of care that define usual care for the initiation of PORT are described (and contrasted with NDURE) in **Table 3**. Usual care consists of clinic-based, clinician-led discussion about the healthcare utilization steps necessary to start PORT. Usual care is not formally theory-based. The HNSCC nurse navigator, a person distinct from the dedicated NDURE navigator, plays a role in delivering usual care (see **Table 3**). As part of usual care, the head and neck nurse navigator identifies and address treatment barriers prior to/up to the initial surgical consultation. Following the initial surgical consultation, the head and neck nurse navigator does not continue providing navigation services along the treatment continuum. Similar to the NDURE navigator, the head and neck nurse navigator is embedded within the head and neck surgery team and participates in weekly multidisciplinary tumor board. Direct contact between the head and neck

nurse navigator and the patient occurs only at the time of initial intake/pre-surgical consultation at the MUSC Head and Neck Oncology clinic. These contacts may be on the telephone prior to (and in preparation for the initial consultation) and/or face-to-face at the time of the initial surgical consultation. The time for these navigation encounters is not proscribed but is noted is generally recorded in the EMR. During the intake head and neck nurse navigator conducts a detailed and comprehensive assessment of patient barriers upon referral to the MUSC clinic.

Table 3. NDURE vs Usual Care

Clinical Tool		
Navigation Encounters	PORT-focused navigation encounters linked to care transitions. There are three manualized navigation encounters with the NDURE navigator. Encounters occur along the cancer care continuum and are linked to key care transitions (presurgical consult, hospital discharge, postoperative clinic visit). During each encounter, the NDURE navigator delivers patient education about timely PORT, addresses challenges with transportation, assesses barriers to timely PORT, and creates or updates and implements the PORT Care Plan.	One generic encounter upon intake. There is one navigation encounter with the head and neck nurse navigator. The encounter occurs upon referral to the MUSC Head and Neck Clinic. During the navigation encounter, the head and neck nurse navigator assesses barriers to treatment and makes appropriate referrals.

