6.1.2 ADMINISTRATION AND/OR DOSING

6.1.2.1 NDURE

NDURE will be delivered in one-on-one, face-to-face sessions between the navigator and the participant in a clinic- or hospital-based setting. The NDURE intervention consists of three navigation encounters (Study Visits 2-4), which are expected to take 30-60 minutes each. The NDURE navigation encounters (Study Visits 2-4) will coincide with the presurgical consult, hospital discharge, and 1st postoperative clinic visit (see Section 1.3, Schedule of Activities). These time points were chosen to facilitate case identification and coordination across key care transitions. Contact beyond the three prescribed sessions will occur with a frequency and modality (e.g. text message, email, etc.) dictated by patient and navigator need. The NDURE intervention will be delivered in the following settings: the MUSC Head and Neck Tumor Center and MUSC hospital. A single dedicated navigator with no competing clinical or administrative responsibilities outside of this trial will deliver the NDURE intervention. Full dose of the NDURE intervention will consist of completing all three navigation sessions. Because the administration schedule and dose of usual care is highly variable, the NDURE intervention will not be dose-matched to usual care on intensity, duration, and/or frequency. Participants in the trial are permitted to interact with other participants after randomization, regardless of treatment allocation. Such encounters may occur in waiting rooms before or after clinic appointments given the single-site design of the trial.

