8 STUDY ASSESSMENTS AND PROCEDURES

8.1 SCREENING PROCEDURES

Once a subject has signed the ICF, an identification number will be assigned to him/her and the study related screening procedures will start. A subject will be randomized into the study after he/she has signed the ICF and all eligibility criteria have been met.

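### The replacement rule inside the full analysis set acts after randomization, has a clear trigger only in NDURE, and leaves unclear whether replaced patients still count

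*Combined protocol and SAP*

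**What the plan says.** Section 9.3 says that the FAS "is the set of all trial participants who enroll and are eligible for the study". The next sentence reads "Patients who enroll but subsequently drop out prior to receiving any of the assigned intervention will be replaced". The FAS is then assigned to the analysis of pre-surgical radiation consultation and "for secondary analyses of both the primary endpoint and secondary endpoints". The dental evaluation set is a restriction of the FAS, and the tooth extraction set is a subset of that.

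For the PORT delay and time-to-PORT sets, the same section says "Analysis will be performed based on assignment at randomization regardless of the intervention received (modified intent to treat". Neither of those sets requires that any intervention was received.

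On timing, Section 8.1 says "A subject will be randomized into the study after he/she has signed the ICF and all eligibility criteria have been met". Section 6.1.2.1 says "The NDURE intervention consists of three navigation encounters (Study Visits 2-4", and the Schedule of Activities puts Visit 2 after allocation. For usual care, Table 3 says of the single nurse-navigator contact: "The encounter occurs upon referral to the MUSC Head and Neck Clinic". The text of Section 6.1.1.2 allows that contact by telephone beforehand "and/or face-to-face at the time of the initial surgical consultation". Section 6.1.2.2 says that no number of sessions defines a full dose of usual care.

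**The concern.** A rule that replaces participants according to what happened after allocation can undo the comparability that randomization provides. That risk is greater when staff know the arm and when the triggering event is defined for one arm only. Here the event is leaving before any assigned intervention. In NDURE it can be read from a visit record. In usual care the plan never says when the intervention starts.

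Pre-surgical radiation consultation is the most exposed endpoint, because the FAS is its main analysis set. Under Section 6.1.1.1 the NDURE navigator alone is responsible for arranging that consultation. A patient who leaves before Session 1 misses the mechanism meant to produce the outcome, so whether that patient counts can matter.

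**Working it through.** **1. Is the rule post-randomization?** It refers to the assigned intervention, so allocation has happened. Section 5.4 separately treats people who consent but are never assigned as screen failures. The rule therefore concerns randomized patients. Section 4.2.1 describes the trial as non-blinded, and Section 6.3 uses permuted blocks of 2 or 4.

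**2. When does the trigger start in each arm?**

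| | NDURE | Usual care |
|---|---|---|
| First assigned contact | Session 1, Visit 2, after allocation | Not defined: intake contact, surgical consultation, or clinician discussion at Visits 2-5 |
| Record of receipt (Section 6.4) | Navigator's visit note, Visits 2-4 | None named |
| Full dose | Three sessions | Stated not to exist |

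Whichever start is chosen for usual care, only NDURE has a record that can show that a patient received nothing.

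**3. What happens to a replaced patient?** Section 9.3 does not say whether that patient stays in the FAS, which arm the replacement enters, or whether both count toward the 170 planned and 180 maximum in Section 9.2.2. If the replaced patient stays and another is simply added, the FAS remains as randomized. If the replaced patient leaves, it does not.

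**4. The plan's own figure.** Section 9.2.2 states 83% power for 75 per arm, 45% versus 25%, two-sided alpha 0.1, pooled Z-test. With a mean rate of 0.35:

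(0.20 × √75 − 1.645 × √(2 × 0.35 × 0.65)) / √(0.45 × 0.55 + 0.25 × 0.75) = (1.732 − 1.110) / 0.660 = 0.944, and Φ(0.944) = 82.7%.

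The figure reproduces. It does not depend on the replacement rule, and the plan states no figure that does.

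**5. Illustration for pre-surgical consultation.** The arm size is 170/2 = 85. The rest is assumed: 3% to 8% of NDURE patients leave before Session 1 (3 to 7 patients), with a consultation rate of 75% in those who stay and 10% in those who leave.

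- 3 leave: (82 × 0.75 + 3 × 0.10)/85 = 72.7% by assignment, against 75% if they are removed. Overstatement 2.3 points.
- 7 leave: (78 × 0.75 + 7 × 0.10)/85 = 69.6%, against 75%. Overstatement 5.4 points.

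In general, the shift is (number removed / 85) × (rate in stayers − rate in leavers). Each 10-point gap contributes 0.35 points (3 removed) to 0.82 points (7 removed). With no gap the shift is zero. If leavers do better than stayers, the sign reverses.

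**6. Illustration for PORT delay re-analysed in the FAS.** Take 75 treated NDURE patients at 25% and 75 usual-care patients at 45%. Add k NDURE patients who left early and have an assumed delay rate r. Keeping them gives a risk difference of 0.45 − (75 × 0.25 + k × r)/(75 + k). Removing them gives 20.0 points. The 75 per arm is the evaluable number and stands in for the FAS size.

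| r | k = 2 | k = 4 | k = 8 | Overstatement if removed |
|---|---|---|---|---|
| 25% | 20.0 | 20.0 | 20.0 | 0 |
| 45% | 19.5 | 19.0 | 18.1 | 0.5 to 1.9 |
| 100% | 18.1 | 16.2 | 12.8 | 1.9 to 7.2 |

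The last row applies the rule in Section 9.4.2 that counts missing status as delayed. That rule is written for evaluable patients, so using it in the FAS is a further assumption.

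**The case against.** A reader might infer that the rule can remove only NDURE patients, because usual care begins at intake before randomization and a usual-care patient could never have received nothing. The documents do not support this. The Schedule of Activities marks usual care at the same post-allocation visits as NDURE. Most of usual care is clinician-led discussion before and after surgery. The nurse-navigator contact may fall at the surgical consultation, and its timing relative to consent is not stated. Care given before allocation is also not naturally assigned care. The safety set treats usual care as something a patient may or may not receive. On that reading a usual-care patient who leaves before Visit 2 also meets the rule.

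A reader might also infer a bias in favour of NDURE. Section 5.5 does raise the possibility that burdened patients opt out, but it is discussing refusal to enrol, and it gives the opposite possibility as well: patients who see few barriers may decline. No direction follows.

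Three further points against the concern are sound. First, the text says replaced, not removed. Second, the statement about analysis regardless of intervention received belongs to the PORT delay and time-to-PORT sets, so the tension is with the FAS's own definition and not with that statement. Third, few early losses may occur: Sections 4.2.3.2 and 5.5 expect attendance and contact near 100% at the session time points, and nothing equates one missed session with dropping out (Section 7.3 requires two missed visits and failed contact attempts). Nor does the plan say that a replacement takes the vacated arm, so damage to the allocation sequence is not shown.

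These points narrow the concern. They do not supply a start for usual care, a matching record of receipt, or the status of a replaced patient in the FAS.

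**Conclusion.** The concern holds in a limited form. The replacement sentence is a post-randomization rule whose trigger is defined and recorded in one arm only, so it can act unequally by arm. It also sits uneasily beside an FAS of all eligible enrolled patients. If replaced patients leave the FAS, four uses are affected: pre-surgical consultation, dental evaluation, tooth extraction, and the FAS re-analyses of the primary and secondary endpoints. For the two dental sets this matters only for early dropouts who still have surgery at the study site.

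Direction and size are unknown. The ranges above (0 to 5.4 points for consultation, 0 to 7.2 points for PORT delay in the FAS) rest on assumed numbers and outcomes of early dropouts, on removal from NDURE only, and on reading replaced as removed. The main analysis of PORT delay uses its own set, by assignment and without a receipt condition, and is not directly affected. This should be corrected, but it does not undermine the primary result.

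**What to change.** Delete the replacement sentence from Section 9.3. State instead that:

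- every eligible randomized patient stays in the FAS in the assigned arm, whether or not any session was received, with outcomes taken from the EMR where consent allows;
- any further enrolment under Section 9.2.2 only adds patients, each through the next scheduled allocation;
- patients who drop out before any intervention are reported by arm.

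Section 9.2.2 already continues enrolment until 75 evaluable patients per arm or 180 in total, so replacement is not needed to reach the target. The EMR is already the source for the consultation and dental endpoints (Section 8.4.6). The cost is a few lines of text and one reporting row. The downside is that the NDURE estimate in the FAS may be slightly less favourable.
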